#### Sample size

Based on sample size and drop-out calculations (power of 90% to detect a 2-point mean group difference in RMDQ score at 3 months and a 30% drop-out rate during follow-up), the main trial aimed for 350 participants but included as many as 461 participants (ref protocol and main), with 300 of these participants from Denmark eligible for this analysis. The SELFBACK trial was powered for the clinical outcome but not the cost-effectiveness analysis.

### Section 4: Statistical analysis

The statistical analyses will be performed based on the intention-to-treat principle; patients are analysed in the group they were allocated. All costs consumed and effects gained within the 9 months of the trial will be calculated for both the SELFBACK intervention group and the usual care group.

#### Costs

Parametric and non-parametric methods appropriate for the data will be used to report descriptive statistics (i.e., mean, standard deviation [SD], lower and upper quartiles, minimum and maximum values) for all resource variables and total costs by trial arm. Binary and categorical variables will be represented in terms of percentages.

Multivariable regression analyses will be used to estimate incremental costs. Because costs are normally right-skewed, general linear models are considered. Two models are estimated; a base-case model, adjusting only for health care costs during the 12-month pre-baseline period, and a model that in addition includes the variables adjusted for in the main trial. The base-case model is estimated both using missing values being imputed and using complete cases.

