### Settings and Participants

We recruited adults who were 18 years or older, had nonspecific LBP within the preceding 8 weeks, scored 6 points or higher on the Roland-Morris Disability Questionnaire (RMDQ) at the time of screening, had consulted a clinician (general practitioner, physiotherapist, or

chiropractor) in the region of Southern Denmark or the Trondheim municipality in Norway or had undergone a clinical examination at an outpatient spine clinic (Spine Centre of Southern Denmark) from March 8 to December 14, 2019.

A total of 461 participants were included, whereby 317 participants from Denmark and 144 from Norway. The current study is based on the data from the 300 Danish participants that provided their unique personal identification numbers, consented to the project, and further research-related use of their data beyond the RCT and are thus eligible for inclusion in this cost-effectiveness analysis. Using the personal identification numbers, data from the RCT were merged with healthcare costs and other relevant register data from Statistics Denmark and from The Danish Health Data Authority.

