### **Randomisation**

We used a web-based trial management system for randomisation. The trial management system concealed group allocation until the randomisation was performed. Participants were randomised in a 1:1 ratio using permuted blocks with random sizes from 4 to 20 and stratified by country (Denmark or Norway) and clinician (general practitioner, physiotherapist, chiropractor, or outpatient clinic).

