### **Patient self-reported data**

Data on self-reported measures were collected in the SELFBACK trial using an online tool at baseline, 6 weeks and 3, 6 and 9 months after the inclusion in the trial. Data used from the questionnaires for this current analysis are socio-demographic characteristics, quality of life measured by EQ5D-5L, Roland-Morris disability questionnaire for LBP-related disability, self-efficacy by the Pain Self Efficacy Questionnaire and variables adjusted for in the main trial

(clinical setting of recruitment [General Practitioner, Physiotherapist, Chiropractor, Outpatient back clinic], age [years], sex [female, male], education [ $<10$  years,  $10\text{--}12$  years,  $>12$  years], duration of current pain episode at baseline [ $\leq 4$  weeks,  $5\text{--}12$  weeks,  $> 12$  weeks] and average pain intensity in the preceding week at baseline [0-10 scale]).

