### Measures of resource use and costs

In Denmark, the Danish National Health Service primarily finance the cost of healthcare utilisation in primary and secondary healthcare. Exceptions to this are chiropractic, physiotherapy, and psychology consultations in primary care, which incur additional out-of-pocket expenses the patient pays.

Individual patient data on primary sector healthcare utilisation and related cost are retrieved from the National Health Service Registry (Sygesikringsregisteret) with services provided by General practitioners, Chiropractors, Physiotherapists, and Medical specialists. Use of secondary sector care utilisation will be retrieved from the National Patient Registry (Landspatientregisteret), including assessments, tests and procedures at Spine centers and rheumatology, neurology, orthopaedic and neurosurgery departments and redeemed prescriptive medication from the National Prescription Registry (Lægemiddeldatabasen).

Costs of prescription medication will be calculated based on prices charged by the pharmacies (excluding VAT). Primary healthcare costs will be valued according to the prevailing fee schedules agreed upon between the providers and the Danish Regions. Hospital treatment costs will be valued with official hospital Diagnosis Related Group (DRG) tariffs provided by the National Health Data Authority. All monetary values will be presented in euros at 2022

cost levels. Therefore, costs will be uplifted to 2022 price levels using the Net Price Index maintained by Statistics Denmark.

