#### Effectiveness measures

Effectiveness measures applied in the cost-effectiveness analyses correspond to the clinical endpoints in the trial. These statistical analyses are described in the clinical trial protocol.

For the EQ-5D-5L index values, central tendency and dispersion measures will be presented for both groups at baseline, 6 weeks, 3, 6, and 9 months after the inclusion in the trial. These

will be presented along with median values and the 25th and the 75th percentiles, as recommended by the EuroQoL Group.

Multivariable regression analyses will be used to estimate incremental QALYs. Because QALYs are normally left-skewed, general linear models are considered. Two models are estimated; a base-case model, adjusting for baseline utility values, and a model that, in addition, includes the variables adjusted for in the main trial. The base-case model is estimated both using missing values being imputed and using complete cases.

Baseline characteristics will be reported as percentages for binary variables and mean values and SDs for continuous variables.

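### The base-case cost and QALY models omit clinician type, the only randomisation stratifier that varies among the Danish participants; if it predicts the outcome, base-case uncertainty is overstated

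*SAP*

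**What the plan says.** SAP, Randomisation: allocation was 1:1 in permuted blocks, "stratified by country (Denmark or Norway) and clinician (general practitioner, physiotherapist, chiropractor, or outpatient clinic". SAP, Settings and Participants: "The current study is based on the data from the 300 Danish participants", so country is constant.

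SAP, Costs, sets two models. The first is "a base-case model, adjusting only for health care costs during the 12-month pre-baseline period". The second adds the covariates of the main trial. SAP, Effectiveness measures, follows the same pattern for QALYs: "a base-case model, adjusting for baseline utility values", then a second model with the main-trial covariates. SAP, Patient self-reported data, lists those covariates, and they include "clinical setting of recruitment [General Practitioner, Physiotherapist, Chiropractor, Outpatient back clinic". The stratifier is therefore collected and used, but not in either base case.

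The base case is the model named in both sections for imputed and for complete-case estimation. The imputation model under SAP, Missing data, lists the outcome at all time points and the allocated group; clinician type is not listed. The model family is left open: "Because costs are normally right-skewed, general linear models are considered". Protocol 5.2 plans the clinical comparison both crude and adjusted for the two stratifiers.

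**The concern.** Stratified blocks force the arms to be balanced on clinician type, so differences between clinician groups cannot contribute to chance differences between arms. A model without clinician type still counts that variation as residual noise, and its standard error is too large whenever the variation is real. A bootstrap that refits the same model inherits the excess, and so does the acceptability curve built from it.

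There is some reason to expect clinician type to matter for cost. Protocol 2.2 describes the Spine Centre as an outpatient hospital seeing patients referred from primary care. The SAP values the two settings differently: "Hospital treatment costs will be valued with official hospital Diagnosis Related Group (DRG) tariffs", whereas "Primary healthcare costs will be valued according to the prevailing fee schedules agreed upon between the providers and the Danish Regions". For QALYs the documents suggest no comparable mechanism.

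What is at stake is precision. The SAP (Sample size) acknowledges that the trial was not powered for the economic question, and this share of the precision can be recovered without new data.

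**Working it through.** The plan states no figure that depends on the base-case covariates, so there is nothing to reproduce.

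**Inputs from the documents.** 317 Danish participants randomised and 300 analysed (SAP, Settings and Participants). Block sizes 4 to 20, four clinician types (SAP, Randomisation). EQ-5D missing for 0, 68, 47, 63 and 68 of 300 at baseline, 6 weeks and 3, 6 and 9 months (SAP, Table 3). Since 68 are missing at a single visit, at most 300 − 68 = 232 have complete EQ-5D.

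**Assumed input.** R², the share of outcome variance explained by clinician type after the baseline covariate: 0, 0.02, 0.05, 0.10, 0.20. The documents give no value.

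**Linear model, all 300.**
- Ratio of reported standard error without and with clinician type: k = 1/√(1 − R²). At R² = 0.10, 1/√0.90 = 1.054.
- Coverage of a nominal 95% interval: 2Φ(1.96k) − 1.
- Largest shift of a point on the acceptability curve: the maximum over z of Φ(kz) − Φ(z).

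**When only part of a stratified sample is analysed.** If a fraction f is kept, unrelated to arm and clinician type, balance is partly lost and the miscalibration falls to 1/√(1 − f·R²). For the complete-case QALY model f = 232/317 = 0.732; at R² = 0.10, 1/√(1 − 0.0732) = 1.039. The remaining reduction in standard error from adjustment is precision gained, not miscalibration corrected. For the 300 kept out of 317, f = 0.946, which changes little: 1.0%, 2.5%, 5.1% and 11.1% at R² of 0.02, 0.05, 0.10 and 0.20.

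| Residual R² (assumed) | SE too wide, all 300 | Coverage | Largest curve shift (points) | Miscalibration, complete-case QALY (232 of 317) |
|---|---|---|---|---|
| 0 | 0% | 95.0% | 0 | 0% |
| 0.02 | 1.0% | 95.2% | 0.2 | 0.7% |
| 0.05 | 2.6% | 95.6% | 0.6 | 1.9% |
| 0.10 | 5.4% | 96.1% | 1.3 | 3.9% |
| 0.20 | 11.8% | 97.2% | 2.7 | 8.2% |

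**Simulation check.** 317 were randomised in four strata of assumed sizes 48, 63, 79 and 127, with 300 kept at random and skewed errors (4,000 runs). Reported over true standard error in the base case was 0.99, 1.00, 1.02, 1.06 and 1.10 across the five values of R². With clinician type added it was 0.99 to 1.01. Under unstratified randomisation at R² = 0.10 the base-case ratio was 0.99, so the excess comes from ignoring the stratification. In separate runs with normal errors, a plain bootstrap of the base-case model was too wide by a factor of 1.02 at R² = 0.05 and 1.13 at 0.20.

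**Gamma cost model, log link, assumed coefficient of variation 1.2** (3,000 runs). Base-case reported over true SD was 1.015, 1.012, 1.038 and 1.116 at R² of 0.02, 0.05, 0.10 and 0.20. The Monte Carlo error on an SD is at least about 1/√(2 × 3,000) = 1.3%, so the first two cannot be told from zero. The mean increment stayed within 0.5% of the mean baseline cost at a true effect of nil, so no bias appeared.

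**The case against.** The strongest reply is that the plan largely handles this. Stratifier-adjusted cost and QALY increments are already pre-specified as the second models, and the protocol has the same crude-then-adjusted structure, so nothing is contradicted. That stands, and it confines the defect to the base case. It does not remove it, because the base case is the model named for imputed and complete-case estimation.

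A second reply is that the effect may be nil. Referral follows the clinician's assessment or treatment (Protocol 2.4), and the care-seeking lies within the preceding 8 weeks (Protocol 2.3). The index contact should therefore already be in the prior-year cost. Only differences in later use remain, and the documents are silent on those. This also stands: every R² above is an assumption. Under the gamma assumptions, R² of 0.20 would need one of four equal clinician groups to cost 2.8 times the others.

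Third, a reader comparing gamma standard errors with and without clinician type would see gaps of 2.8%, 6.3%, 12.6% and 26.3% and might take them as the size of the error. They are not. They combine miscalibration with true precision gain and with an adjusted standard error that is itself slightly small. At R² = 0.10, reported over true SD after adjustment is 1.038 × 1.056/1.126 = 0.97, where 1.056 is the ratio of true SDs without and with clinician type; at 0.05 it is 1.012 × 1.033/1.063 = 0.98.

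Finally, the imputation list in the SAP need not be exhaustive, and no effect of leaving clinician type out of it has been estimated.

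**Conclusion.** Both base-case models omit the one stratifier that varies in the analysed sample. The consequence is conditional: if clinician type explains outcome beyond the baseline covariate, base-case uncertainty is overstated; if it does not, nothing is wrong with the standard errors. For residual R² up to 0.05 the linear-model excess is at most 2.6%, and at 0.20 it is 11.8%. It is smaller for complete-case QALYs (1.9% and 8.2%), provided missingness is unrelated to arm and clinician type. For a gamma cost model it is clearly visible only from R² of about 0.10 (3.8%, and 11.6% at 0.20). The stratum sizes and the coefficient of variation in the simulations are also assumptions.

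A reader might infer that the incremental costs, QALYs or ICER are biased, or that the economic conclusion is unsafe. The documents support neither: stratified 1:1 allocation keeps the increments unbiased and the error is conservative. Nor do they support saying outright that the intervals are too wide, since no R² is given. The SAP could also state which increments feed the ICER, and whether the crude or adjusted RMDQ and PSEQ effects are used. Those are clarifications and not part of this error.

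The change is worth making because it is nearly free, not because the damage is large.

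**What to change.** Add clinician type (three indicator terms) to both base-case models, keeping prior-year cost and baseline utility. Include it in the imputation model so that this matches the analysis model. In each bootstrap sample, resample within arm and refit the cost and QALY models with clinician type included. Keep the planned second models and the complete-case analysis as they are.

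The cost is SAP wording and three degrees of freedom out of 300 in each model. No new data are needed, because clinician type was recorded for randomisation and is already listed among the main-trial covariates. If clinician type predicts nothing, the simulated linear-model standard error is essentially unchanged (ratio 1.000 to 1.001).

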### Objectives

The current health-economic analysis is based on a subset of participants in the SELFBACK RCT and aims to evaluate the 9 months' cost-effectiveness and cost-utility of the SELFBACK system in addition to usual care versus usual care alone.

The specific objectives are:

- (1) to assess mean per-patient additional costs associated with the SELFBACK system compared to usual care
- (2) to assess the incremental effectiveness of the SELFBACK system compared to usual care, in terms of quality of life, LBP-related disability and self-efficacy
- (3) estimate the incremental cost-effectiveness/utility of the SELFBACK system compared to usual care

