### Economic evaluation

This cost-effectiveness analysis will be conducted from a national healthcare perspective and a limited societal perspective including effects on formal productivity. We merge individual self-reported patient data with Danish national registries. An overview of databases and costs is provided in Table 2.

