#### Formal productivity costs

Data on lost formal production, measured in terms of long-term (>4 weeks) sickness absence, will be retrieved from the Danish Register for Evaluation of Marginalization (DREAM). Productivity loss was estimated using the Human Capital method based on weeks of absence from work for participants who were not retired. The value of forgone earnings is assessed by the average gross wage.

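### The cost models adjust for prior health care cost but not for prior sickness absence, so the societal cost difference may lose some precision (not bias)

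*SAP*

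**What the plan says.** The SAP (Section 3, Economic evaluation) sets a national health care perspective and "a limited societal perspective including effects on formal productivity". Under Formal productivity costs it names the source and the valuation: "Data on lost formal production, measured in terms of long-term (>4 weeks) sickness absence, will be retrieved from the Danish Register", and "Productivity loss was estimated using the Human Capital method based on weeks of absence from work for participants who were not retired".

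Section 4, Costs, is the only place that specifies models for incremental cost. There are two. The first is "a base-case model, adjusting only for health care costs during the 12-month pre-baseline period". The second adds the main-trial covariates, which Patient self-reported data lists as recruitment setting, age, sex, education, length of the current pain episode and average pain intensity. Sickness absence is not among them. On the model family the section says: "Because costs are normally right-skewed, general linear models are considered". No link function is given.

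For QALYs, the base-case model under Effectiveness measures adjusts for the baseline value of the same measure, utility.

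**The concern.** The SAP adjusts each outcome for its own earlier value in two of three cases: health care cost for prior health care cost, and QALYs for baseline utility. Productivity cost is the component that turns the health care perspective into a societal one, and it has no such term. Past long-term absence is a natural predictor of future long-term absence, and DREAM is already a planned source.

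The first objective is "to assess mean per-patient additional costs associated with the SELFBACK system compared to usual care". The SAP states under Sample size that "The SELFBACK trial was powered for the clinical outcome but not the cost-effectiveness analysis", and 300 people are available. Costs of absence lasting more than four weeks are concentrated in a few participants, so the societal difference is likely to be imprecise. A prespecified baseline covariate is a cheap way to recover some of that precision.

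**Working it through.** **Plan's own figure.** There is none to reproduce. The documents give no standard error (SE), power or sample size for a cost difference, and no absence rate, correlation or cost share. Every input below except n = 300, 1:1 allocation and the covariate lists is an assumption.

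**Step 1: bias.** Allocation was randomised 1:1 (SAP, Randomisation), so leaving out a baseline covariate does not bias the difference. In a simulation of 4,000 trials with n = 300, skewed costs and a true difference of -500, the mean estimate was -496.7 without prior absence and -496.5 with it (Monte Carlo error about 9).

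**Step 2: precision, base-case model.** Let s be productivity's share of the residual variance of total societal cost, and r the correlation of the prior-absence covariate with productivity cost. The base-case model has three parameters (300 - 3 = 297 residual degrees of freedom), and adding the covariate leaves 296. The relative change in SE is

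sqrt((1 - s × r²) × 297/296) - 1.

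Example, s = 0.5 and r = 0.6: 1 - 0.5 × 0.36 = 0.82; 0.82 × 1.00338 = 0.8228; the square root is 0.907, so -9.3%.

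| r | s = 0.25 | s = 0.50 | s = 0.75 |
|---|---|---|---|
| 0 | +0.2% | +0.2% | +0.2% |
| 0.3 | -1.0% | -2.1% | -3.3% |
| 0.6 | -4.4% | -9.3% | -14.4% |

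As an equivalent sample size at s = 0.5: 300/(1 - 0.045) = 314 at r = 0.3, and 300/0.82 = 366 at r = 0.6.

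**Step 3: precision, second model.** The main-trial covariates add 10 parameters (setting 3, age 1, sex 1, education 2, episode duration 2, pain 1), making 13 and a factor of 287/286. If they already absorb 0, 25, 50 or 75% of r², then at s = 0.5 the changes are -2.1, -1.5, -1.0 and -0.4% at r = 0.3, and -9.3, -6.8, -4.4 and -2.1% at r = 0.6.

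**Step 4: simulation with skewed costs and a yes/no indicator.** Assumptions: 150 per arm; 15% retired with no absence; 10% with prior absence; 9-month absence risk with/without prior absence of 5/5, 30/6, 50/4 or 75/3%; absences of 5 to 39 weeks; lognormal health care cost. The correlation between prior and follow-up weeks is then 0.01, 0.23, 0.42 and 0.60. Change in the true standard deviation of the estimate, with productivity in a linear model:

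| Productivity share | r = 0.01 | 0.23 | 0.42 | 0.60 |
|---|---|---|---|---|
| 0.18 to 0.32 | +0.1% | -1.0% | -3.3% | -8.3% |
| 0.45 to 0.64 | +0.1% | -2.4% | -8.1% | -17.3% |
| 0.81 to 0.90 | +0.1% | -3.9% | -12.0% | -23.8% |

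The last column exceeds what Step 2 gives at r = 0.6 because the indicator is more strongly correlated with follow-up weeks than prior weeks are. For 75/3%: P(absence) = 0.10 × 0.75 + 0.75 × 0.03 = 0.0975. The covariance is 22 × (0.075 - 0.10 × 0.0975) = 1.4355. The variance of weeks is 0.0975 × (22² + 102) - (0.0975 × 22)² = 52.5, so the SD is 7.25. The indicator's SD is 0.3. The correlation is 1.4355/(0.3 × 7.25) = 0.66. Putting r = 0.66 and s = 0.90 into Step 2 gives about -22%, close to the simulated value.

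**Step 5: one model or two.** In ordinary least squares with the same covariates, the group coefficient for total cost is exactly the sum of the coefficients for its components. A separate linear productivity model therefore gains nothing over one linear total-cost model.

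**Step 6: link.** With an assumed 30% cut in absence risk (30/6, 50/4 and 75/3%), the linear form with the indicator recovers 95, 98 and 99% of the true societal difference. A gamma log-link model of total cost with the indicator recovers 96, 81 and 65% (Monte Carlo error about 3 points). The log-link model without the indicator did not under-recover. The distortion comes from adding the indicator on the log scale.

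**Step 7: bootstrap intervals.** In 440 runs of 300 replicates, coverage without/with the indicator was 94.3/94.1% and 94.5/94.1% at 30/6 (no effect, effect), and 92.5/91.6% and 93.4/93.4% at 75/3 (Monte Carlo error about 1.2 points). The check is small, and the SAP plans 1000 replicates. It shows no material loss from the indicator, though coverage is somewhat below 95% either way in the extreme case.

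**The case against.** Under randomisation any prespecified covariate set gives a fair comparison, and the SAP prespecifies two. Leaving out one possibly prognostic variable is a legitimate choice, and the SAP admits the limited power. All of that stands, and it is why this is a suggestion and not a correction.

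Every size above rests on assumed inputs. The largest gain needs a 75% against 3% absence risk and productivity at 81 to 90% of cost variance; at weak correlations the gain is 1 to 4%, and less in the second model. That also stands.

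Three stronger readings are tempting, and the documents do not support them:

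- **That the societal cost difference is biased.** Allocation was randomised, and chance imbalance in prior absence is part of the sampling error that the interval already covers.
- **That the SAP has no model for societal cost.** The models under Costs are for incremental costs in general and can be read as covering the total under either perspective. If they are linear, a separate productivity model would add nothing (Step 5).
- **That the SAP's open link distorts the estimate.** The shortfall in Step 6 arises only when the indicator is put into a log-link model of the total, which the SAP does not propose.

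Finally, Table 2 of the SAP, described as an overview of databases and costs, is not in the available text. A pre-baseline DREAM window may already be planned, so its absence here cannot be held against the plan.

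**Conclusion.** The point holds as an optional improvement. Neither cost model adjusts for prior sickness absence, although the societal perspective adds its cost and the SAP gives health care cost and QALYs the corresponding baseline term. The consequence is a possible loss of precision.

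The size cannot be taken from the documents. Under the assumptions above, adding the indicator in a linear model changes the SE by about +0.2% if it is uninformative, by -1 to -4% at a correlation of about 0.25 to 0.3, and by about -4 to -24% at about 0.6, depending on productivity's share of cost variance. The gain shrinks in the second model to the extent that the main-trial covariates already carry the signal. Confidence is high on what the text says and low on where in this range the trial lies.

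**What to change.** For the societal perspective:

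- State that the total-cost difference is estimated in a linear (identity-link) model.
- Add to both cost models a yes/no indicator of any long-term absence recorded in DREAM in the 12 months before baseline. Code it zero for anyone with no recorded absence, including the retired.
- Refit with the same covariates in every bootstrap replicate.
- Use a separate linear productivity model, added to the health care difference, only if health care cost is modelled with another link.
- Do not add the indicator to a log-link model of total societal cost.

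The cost is a few sentences in the SAP, a 12-month DREAM look-back if none is planned, and an SE about 0.2% larger if the indicator proves uninformative. The choice should be fixed before cost data are seen. The SAP says (Section 1) that it was registered before register data were retrieved; if those data are now held, label the change as a post-registration addition.
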